### **6.1. STUDY DAY AND PERIOD DAY**

Two different types of study days will be calculated for this study:

1. Study Day will be calculated based on the date of the first dose of study drug and will be used to

show start and stop days of assessments and events during the study. Study Day 1 will be the day of the first dose of study drug.

2. Period Day will be calculated based on the date of the first dose of study drug during the period in which the assessments or events are performed or occur to show start and stop days of assessments or events during the treatment period.

Study Days will be calculated as follows:

- Study Day = (date of assessment or event – date of first dose of study drug) if the date of assessment or event is before the date of first dose of study drug
- Study Day = (date of assessment or event – date of first dose of study drug) + 1 if the date of assessment or event is on or after the date of first dose of study drug

Period Days of each treatment period will be calculated as follows:

- Screening Period Day = (date of assessment or event – date of first dose of study drug during period 1)
- Period Day = (date of assessment or event – date of first dose of study drug during the period) + 1 for periods 1, 2, 3, and 4
- Safety Follow-up Period Day = (date of assessment or event – end date of the last treatment period completed prior to the Safety Follow-up Period) + 1

[figure not shown]
## 6.2. BASELINE

Unless otherwise specified, the Baseline will be defined as the last non-missing measurement performed prior to the date of first dose of study drug in period 1 (including unscheduled and retest assessment).

## 6.3. WINDOWING CONVENTIONS

[figure not shown]
Scheduled assessments will be summarized/analyzed by nominal visits. Unscheduled and Early Termination visits will be mapped by the window then summarized/analyzed using the rules below (Table 4).

[figure not shown]

**Table 4 Visit Windows for Unscheduled and Early Termination Assessments and Measurements Recorded At Study Visits**

Visit	Week Assigned	Target Day	Visit Window	
			Lower Study Day	Upper Study Day
1	Screening	N/A	(Date of first dose of study drug during period 1) – 3 i.e., Day -3	(Date of first dose of study drug during period 1) – 31 i.e., Day -31
2	Baseline	-1	(Date of first dose of study drug during period 1) – 2 i.e., Day -2	(Date of first dose of study drug during period 1) – 1, i.e., Day -1
3	Week 1	7	Date of first dose of study drug during period 1 i.e., Day 1	
 
• (Study Day of the first dose of study drug during period 2) – 1 if subject received treatment during period 2
 
• Study Day of the last dose of study drug during period 1 if subject did not receive any study drug after period 1
 

4	Week 2	14	Study Day of the first dose of study drug during period 2	
 
• (Study Day of the first dose of study drug during period 3) – 1 if subject received treatment during period 3
 
• Study Day of the last dose of study drug during period 2 if subject did not receive any study drug after period 2
 

5	Week 3	21	Study Day of the first dose of study drug during period 3	
 
• (Study Day of the first dose of study drug during period 4) – 1 if subject received treatment during period 4
 
• Study Day of the last dose of study drug during period 3 if subject did not receive any study drug after period 3
 

6	Week 4	28	Study Day of the first dose of study drug during period 4	Study Day of the last dose of study drug during period 4
7	Safety Follow-up	35	Study Day of the last dose of study drug across all periods + 1	Whichever is the latest between the Study Day of the last dose of study drug across all periods + 8 and Study Day of the early termination Visit

If multiple assessments or measurements are recorded within a single visit window (including unscheduled, repeated, and retest assessments or measurements as well as early discontinuation data), the following rules will be applied to determine the result from which assessment or measurement will be used for the summaries for that visit window.

- If there are two or more results within the same visit window, then the non-missing observation closest to the target day will be used in the analysis.
- If two observations are collected on the same day and this day is the closest to the target day, then the non-missing observation with the latest collection time will be included in the analysis.

If a visit window does not contain any observations, then the data will remain missing.

Listings will include scheduled, unscheduled, repeated, retest, and early termination data.

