**Subjects enrolling in the study after Amendment 2 implementation will not undergo PK evaluation.**

On admission to the investigative site in the morning (at approximately 8:00 AM) on Days 7 ( $\pm 1$ ), 14 ( $\pm 1$ ), 21 ( $\pm 1$ ), and 28 ( $\pm 1$ ), complete the following (as listed in Appendix 3):

- Record all concomitant medications, including OTC medications, health, and dietary supplements taken since the last visit. Record all AEs. Verify PD medications, sleep medications allowed by the protocol, and study drug (as specified in [Section 5.3](#) of the protocol) were taken and continue to be taken appropriately. For subjects currently receiving treatment for OSA, review OSA therapy device usage to ensure adequate compliance.
- Administer the ESS Questionnaire.
- Administer the MDS-UPDRS (Parts III and IV). When feasible, the MDS-UPDRS (Parts III and IV) is to be performed on the same study day and approximate same time for each subsequent visit while the subject is in the “on” state.
- Complete the CGIc.
- Perform physical examination.
  - Obtain weight in ordinary indoor clothes (without shoes).
- Approximately 1 hour before dosing, obtain vital signs (systolic and diastolic blood pressure [seated and standing], pulse rate [seated and standing], respiratory rate, and body

temperature), including at least 2 sets of blood pressure and pulse rate measurements in the seated position after the subject has been resting and seated for at least 5 minutes.

Next, standing blood pressure and pulse rate should be taken at 1 and 3 minutes after the subject has been standing.

- 12-lead ECG after the subject has been resting supine for at least 5 minutes.
- Obtain safety laboratory blood samples for serum chemistry and hematology tests and a urine sample for urinalysis.
- Obtain a urine sample for a pregnancy test for all females of childbearing potential (see [Table 1](#) for definitions of childbearing potential).
- Complete breath alcohol screen test.
- Observe study drug administration by the subject.
- Approximately 15 minutes after dosing, subjects may be served a light breakfast. Breakfast should be completed within 15 to 20 minutes.

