## 7.4 Follow-up (Day 35 [ $\pm 1$ day]) (For Subjects in Both Groups 1 and 2)

At the Follow-up Visit, perform the following:

- Record all concomitant medications, including OTC medications, health, and dietary supplements taken since the last visit.
- Complete physical examination.
  - Obtain weight in ordinary indoor clothes (without shoes).
- Obtain vital signs (systolic and diastolic blood pressure [seated and standing], pulse rate [seated and standing], respiratory rate, and body temperature), including at least 2 sets of blood pressure and pulse rate measurements in the seated position after the subject has been resting and seated for at least 5 minutes. Next, standing blood pressure and pulse rate should be taken at 1 and 3 minutes after the subject has been standing.
- Obtain a 12-lead ECG after the subject has been resting supine for at least 5 minutes.
- Obtain safety laboratory blood samples for serum chemistry and hematology tests and a urine sample for urinalysis.
- Obtain a urine sample for a pregnancy test for all females of childbearing potential (see [Table 1](#) for definitions of childbearing potential).
- Complete breath alcohol screen test.
- Administer the C-SSRS Since Last Visit Version and record the results.
- Complete the ESS Questionnaire.
- Document any AEs that occurred since the last visit. Document the outcome of any ongoing AEs.

Unless any safety issues are identified that require follow-up, the study will be considered completed and the subject will be discharged from the study. Subjects will be instructed to follow-up with their healthcare provider regarding the resumption of any medications that were discontinued prior to study participation.

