## 17.1. ADVERSE EVENTS

Adverse events will be coded to SOC and PT using the MedDRA dictionary (version 18.0) and will be classified as follows:

- **Prior AEs** are defined as AEs that started on or after the signature of the informed consent but prior to the first dose of study drug (i.e., first dose in Period 1) and have not worsened in severity on or after the first dose of study drug;
- **Treatment-emergent adverse events (TEAEs)** are defined as any AEs that started or worsened in severity on or after the first dose of study drug;

Only TEAEs will be summarized; listings will include all AEs (see APPENDIX 1 for handling of partial dates for AEs). AEs will be reported under the treatment group being received when AE first occurs/worsens. Should an AE with a partially missing onset date can be assigned to more than one treatment group, it will be reported under the active treatment group with the lowest dose. For TEAEs that started during the safety follow-up period, TEAEs will be attributed to the last treatment group received in the study.

An overall summary of number and percentage of subjects within each of the categories described in the following subsections (e.g., all TEAEs, SAEs, AEs leading to discontinuation of study drug, etc.) will be provided. A similar overall summary will be presented for the subset of TEAEs that started during the safety follow-up period.

For TEAEs summarized by SOC and PT, SOC will be sorted in alphabetical order and the PTs within each SOC will be sorted in descending frequency order for the pooled JZP-110 treatment group. For PT only tables, incidence will be sorted similarly to the PTs in the summaries by SOC and PT.

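### Early Termination labs, weight, temperature and respiratory rate taken after the day of last dose are filed under Safety Follow-up, not under the dose on which the subject stopped

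*SAP*

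**What the plan says.** **Assignment.** Under SAP Section 6.3, scheduled assessments keep their nominal visit, whereas "Unscheduled and Early Termination visits will be mapped by the window then summarized/analyzed using the rules below".

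**On-treatment windows (SAP Table 4).** For a subject who goes on to another period, the window runs to the day before that period's first dose. For a subject who does not, the Week 1 window ends on "Study Day of the last dose of study drug during period 1 if subject did not receive any study drug after period 1". Weeks 2 and 3 are worded alike, and Week 4 always ends on the last dose.

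**Safety Follow-up window.** It opens at "Study Day of the last dose of study drug across all periods + 1" and closes on the later of two days, last dose across all "periods + 8 and Study Day of the early termination Visit". Its target is fixed at Study Day 35. When several results share a window, "then the non-missing observation closest to the target day will be used in the analysis".

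**Visits.** Protocol Section 7.5 provides the ET visit for subjects who will take no more study drug. Sections 6.14.5 and 7.5 ask them back one week later, if willing. Protocol Section 3.1 places follow-up about 7 days after the last dose.

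**Summaries.** SAP Section 17 presents safety by treatment group. Labs are summarized by visit (17.2); temperature, respiratory rate and weight at end of period (17.4.1); ECGs and seated blood pressure and pulse mainly at post-dose timepoints (17.3, 17.4.2). For adverse events, Section 17.1 says: "For TEAEs that started during the safety follow-up period, TEAEs will be attributed to the last treatment group received in the study".

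**The concern.** Safety and tolerability are the primary objective, and a subject who stops because of a dose is especially informative about it. Three features make the window rule hard to defend.

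- **Time since dose.** At scheduled visits the instruction "Obtain safety laboratory blood samples for serum chemistry and hematology tests and a urine sample for urinalysis" comes before observed dosing (Protocol Sections 7.2.2 and 7.3.2), so labs are usually drawn about 24 hours after the previous dose. An ET lab on the day after the last dose is comparable, yet it is not counted on treatment.
- **Dependence on withdrawal.** In Periods 1 to 3 a value taken the day after the last dose can fall inside the period window for a subject who has not yet started the next period, but not for one who withdraws.
- **Mismatch with adverse events.** An event starting in follow-up is credited to the last treatment, while the ET lab value behind it may not be.

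Labs have little backup. SAP Section 3.6 drops the by-treatment tabulation of abnormal values and leaves a listing, so the by-visit descriptive summary is the only by-dose lab display.

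**Working it through.** **Notation.** L is the study day of last dose, ET the day of the ET visit, and FU the day of the follow-up visit. The limits come from Table 4. The gap between L and ET is not in the documents; I take 0 to 7 days as an assumption. For FU I use both protocol readings, ET + 7 and L + 7.

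**Check on completers.** With L = 28 the Safety Follow-up window is Days 29 to 36, which contains Day 35 ± 1. The table works as intended for them.

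**Step 1: which window the ET visit falls in.** Mid-period last-dose days are 1 to 27 without 7, 14 and 21, which is 24 days. With 8 possible gaps there are 24 × 8 = 192 scenarios.

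- Gap 0: ET = L stays in the dose week, 24 of 192.
- Gap 1 to 7: ET ≥ L + 1 goes to Safety Follow-up, 168 of 168.

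This step needs no follow-up visit.

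**Step 2: whether an attended follow-up visit replaces the ET record.** The record nearer Day 35 is used.

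- *FU = ET + 7.* FU is nearer whenever ET is Day 31 or earlier (at ET = 31 the distances are 4 and 3; at ET = 32 they are 3 and 4). If both records compete, FU is used in 162 of 168. But FU lies inside the window only if L + gap + 7 ≤ L + 8, that is, gap ≤ 1. So 24 of the 162 are settled by the text. The other 162 − 24 = 138 have FU outside the window; it is still nominal Visit 7, and the SAP does not say which record is used.
- *FU = L + 7.* FU is always inside the window and is used in 24 × 6 = 144 of 168. In the remaining 24 (gap 7), ET and FU fall on the same day.

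| L | ET | FU | Window | Distances from Day 35 (ET, FU) | Result |
|---|---|---|---|---|---|
| 10 | 11 | 18 | 11–18 | 24, 17 | FU used |
| 10 | 12 | 17 | 11–18 | 23, 18 | FU used |
| 10 | 12 | 19 | 11–18 | 23, 16 | FU outside window; not settled |

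In all three, Week 2 holds no ET record.

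**Step 3: how many subjects.** SAP Section 3.4 plans 49 randomized and 40 completing: 49 − 40 = 9 (18.4%). In Sequences A and B, 42 − 34 = 8 (19.0%). Spread evenly over four periods, 8 / 4 = 2 of 42 (4.8%) per period. These are upper limits: they count everyone who leaves, at any point and for any reason.

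**Step 4: effect of moving the limit to L + 1.** ET records in the dose week rise from 24 to 24 + 24 = 48 of 192. The other 144 need a row of their own.

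The counts are scenarios on an assumed grid, not expected patients.

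**The case against.** **The mapping is deliberate and pharmacologically reasonable.** The Safety Follow-up limit is stretched to reach the ET day, so these visits were meant to go there. Protocol Section 1.3.1 gives a half-life of 5 to 7.6 hours. The fraction remaining is 0.5^(24/5) = 3.6% to 0.5^(24/7.6) = 11.2% at 24 hours, and 0.1% to 1.3% at 48 hours. This stands for ET visits two or more days after the last dose. It does not separate an ET lab at last dose + 1 from a scheduled pre-dose lab. That comparison is itself approximate, since Group 1 labs may be drawn the day before the visit (Protocol Appendix 3).

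**ECGs and blood pressure.** A reader might infer that the window also removes these. The documents do not support that as the cause: their main summaries use post-dose timepoints, and an ET visit has none. Moving the window alone would not bring them in.

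**Other safety data.** A reader might infer that withdrawals' safety data as a whole leave the by-dose summaries. They do not. Adverse events, serious events and discontinuations due to events are attributed by treatment, and Protocol Section 6.14.1 makes clinically significant lab, ECG, vital sign and examination changes adverse events. Listings keep ET data, and earlier completed periods keep theirs.

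**Replacement is not certain.** It needs an attended follow-up visit. Without one, the ET value stands as the Safety Follow-up value. When follow-up falls after last dose + 8, the text leaves the outcome open.

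**Conclusion.** The point holds for labs, weight, temperature and respiratory rate of subjects who stop mid-period and have an ET visit at least one day after the last dose. Those values leave the dose-week summary in every such case. With an attended follow-up they will often enter no summary at all, although the SAP does not settle this for follow-up after last dose + 8. The SAP also does not say under which dose, if any, Safety Follow-up lab results appear, and the output shells are not among the documents.

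At most about 9 planned non-completers are exposed (8 in Sequences A and B), and probably fewer. Subjects seen for ET on the day of last dose, or stopped at a scheduled end-of-period visit, are unaffected.

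A reader might infer a loss of up to 19% of the observations at one dose. That needs all 8 non-completers in Sequences A and B to stop mid-period on the same dose with a delayed ET visit; for the values to enter no summary, all must also return for follow-up. Nothing in the documents supports that combination, and the 4.8% per period carries the same assumptions about delay. This is an inexpensive improvement to summaries that serve the primary objective, not a defect that hides safety signals.

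**What to change.** In SAP Table 4 and Section 6.3:

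1. Extend the upper limit of the last treated period to last dose + 1 day for ET labs, weight, temperature and respiratory rate, and start Safety Follow-up after that for these records.
2. Show later ET values of these measures, and all ET ECG and seated blood pressure and pulse values, in a separate Early Termination row under the last dose received, in line with the adverse event rule.
3. State that the Safety Follow-up visit does not replace the ET record, including when follow-up falls after last dose + 8. State also which dose column, if any, Safety Follow-up rows belong to.

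The cost is SAP wording and programming, with no new data collection. The downside is that some ET values are at trough or off drug, so acute effects may be understated; a footnote giving days since last dose would make this visible.

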### 6.14.5 Removal of Subjects from the Trial or Study Drug

All subjects are free to withdraw from participation in this study at any time, for any reason, and without prejudice. The investigator must withdraw any subject from the study if the subject states that he/she wants to stop participating in the study.

The investigator, Jazz Pharmaceuticals or its designee may remove a subject from the study at any time and for any reason.

If any of the criteria below are met during the study, study drug administration must be stopped and the subject must be discontinued from the study.

- Active suicidal ideation or behavior (e.g., a positive response to Question 4 or 5 on the C-SSRS)

- 3-fold or greater elevation above the ULN of ALT or AST accompanied by an elevation of serum total bilirubin greater than 2 times the ULN
- Liver enzyme (AST, ALT) value greater than or equal to 5 times the ULN
- Serum creatinine  $\geq 2$  mg/dL
- Positive urine drug screen (unless due to a prescription medication that is allowed by the protocol)
- Positive pregnancy test
- Subject demonstrates a QTcF interval of  $>450$  msec for males and  $>470$  msec for females (determinations should be based on at least 2 ECG recordings performed in close proximity prior to study drug discontinuation)
- Subject experiences a serious adverse event that is considered related to study drug or procedure

For all subjects who prematurely discontinue, an attempt should be made to perform all early termination assessments as indicated in [Section 7.6](#). Subjects should be asked to return 1 week later for a Safety Follow-up visit.

The specific reason for the discontinuation should be documented on the termination eCRF. If a subject withdraws informed consent, the specific reason for withdrawing the informed consent should be stated.

Adverse events resulting in termination will be followed to the satisfactory resolution and determination of outcome as ascertained by the investigator (and/or Jazz Pharmaceuticals or its designee). The data will be recorded on the appropriate eCRF.

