### 17.3. ECG EVALUATIONS

The following ECG parameters will be reported for this study based on core laboratory values:

- HR (beats per minute [bpm])
- RR interval (msec)
- PR interval (msec)
- QRS interval (msec)
- QT interval (msec)
- QT Fridericia's correction (QTcF) interval (msec) [derived]
- QT Bazett's correction (QTcB) interval (msec) [derived]
- Overall evaluation of ECG:
  - Normal
  - Abnormal, not clinically significant
  - Abnormal, clinically significant

The following summaries will be provided based on SAF for ECG data:

- Observed values and change from Baseline to end of period post-dose timepoint (for quantitative measurements)
- Observed values and change from end of period pre-dose timepoint to end of period post-dose timepoint (for quantitative measurements)
- Incidence of markedly abnormal criteria from Baseline to end of period post-dose timepoint (refer to Section 17.3.2 for details) by gender
- Incidence of markedly abnormal criteria from end of period pre-dose timepoint to end of period post-dose timepoint (refer to Section 17.3.2 for details) by gender
- Shift from Baseline to end of period post-dose timepoint in ECG overall evaluation by gender
- Shift from end of period pre-dose timepoint to end of period post-dose timepoint in ECG overall evaluation by gender

- Incidence of subjects for which their ECG overall evaluation improved, remained unchanged or worsened from Baseline to end of period post-dose timepoint by gender
- Incidence of subjects for which their ECG overall evaluation improved, remained unchanged or worsened from the end of period pre-dose timepoint to the end of period post-dose timepoint by gender
- Incidence of subjects with at least one ECG diagnosis by diagnosis category (i.e., rate/rhythm, conduction abnormalities, changes in ST segment, axis, chamber enlargement, myocardial infarction, and miscellaneous) and diagnosis by visit, timepoint, and gender

The following listings will be provided:

- Listing of subjects with any observed QT, QTcB, or QTcF values >450 msec and/or change from Baseline in QT, QTcB, or QTcF >30 msec
- Listing of subjects with any abnormal ECG overall evaluation

The following figures will be provided:

- Line plot of mean observed values across visit by sequence and treatment group;

[figure not shown]

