### 17.4.2. SEATED BLOOD PRESSURE AND PULSE RATE

The average of all measurements collected during the Baseline visit and of all measurements collected during the end of period visit post-dose timepoints will be computed and the following summaries will be provided:

- Average observed values and average change from Baseline to the end of period visit;
- Shift from Baseline to end of period visit when average observed values are categorized into Low/Normal/High (refer to Table 6);
- Incidence of subjects with average change from Baseline to end of period visit meeting the following criteria:
  - Decrease/increase in SBP  $\geq 10$ ,  $\geq 20$ , and  $\geq 30$  mmHg
  - Decrease/increase in DBP  $\geq 10$ ,  $\geq 20$ , and  $\geq 30$  mmHg
  - Decrease/increase in pulse rate (HR)  $\geq 15$  and  $\geq 30$  beats per minute

The average of the 2 (or 3, when applicable) measurements collected during each end of period visit pre-dose and post-dose timepoints will also be computed and the following summaries will be provided:

- Average observed values and average changes from the end of period visit pre-dose timepoint to each end of the period visit post-dose timepoint;

- Average observed values and average changes from each baseline visit timepoint to time-matched end of period visit timepoint, where the 0-hour baseline timepoint is matched with the pre-dose end of period visit timepoint, the 2-hour baseline timepoint with the 1-hour post-dose end of period timepoint, the 3-hour baseline timepoint with the 2-hour post-dose end of period visit timepoint, and the 5-hour baseline timepoint with the 4-hour post-dose end of period timepoint;
- Shift from end of period visit pre-dose timepoint to each end of period post-dose timepoint when average observed values are categorized into Low/Normal/High (refer to Table 6);
- Shift from each baseline visit timepoint to time-matched end of period visit timepoint when average observed values are categorized into Low/Normal/High;
- Incidence of subjects with average change from end of period pre-dose timepoint to each end of period visit post-dose timepoint meeting the criteria described above;
- Incidence of subjects with average change from each Baseline timepoint to time-matched end of period visit timepoints meeting the criteria described above

The following listings will be provided:

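### SAP 6.3 and 17.3 leave superseded and mid-period abnormal ECGs out of the by-dose incidence and shift tables

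*SAP*

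**What the plan says.** SAP 6.3 summarises scheduled assessments by nominal visit and maps unscheduled and early-termination results into the windows of Table 4. Each treated window runs from the first dose of a period to the day before the first dose of the next. The selection rule opens "If multiple assessments or measurements are recorded within a single visit window (including unscheduled, repeated, and retest assessments or measurements" and goes on to name early discontinuation data. With two or more results in a window, "then the non-missing observation closest to the target day will be used in the analysis" (target days 7, 14, 21 and 28). With two on that same closest day, "then the non-missing observation with the latest collection time will be included in the analysis". Incidence and shift tables are not exempted. Unselected values are kept elsewhere: "Listings will include scheduled, unscheduled, repeated, retest, and early termination data".

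SAP 17.3 plans "Incidence of markedly abnormal criteria from Baseline to end of period post-dose timepoint", with the limits set in 17.3.2 (QT, QTcB and QTcF above 450, 480 and 500 msec; QT and QTcF increases above 30 and 60 msec). The ECG shifts end at the same post-dose timepoint. An exceedance at any other time appears only in a "Listing of subjects with any observed QT, QTcB, or QTcF values >450 msec" or with a change above 30 msec.

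Seated blood pressure and pulse have their own rule in SAP 17.4.2. "The average of the 2 (or 3, when applicable) measurements collected during each end of period visit pre-dose and post-dose timepoints" is computed, and so is the average over all post-dose readings at the visit.

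For a QTcF-based discontinuation, Protocol 6.14.5 says that "determinations should be based on at least 2 ECG recordings performed in close proximity prior to study drug discontinuation".

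**The concern.** Safety is the primary objective and is assessed by description alone (Protocol 9.2), so the by-dose counts of abnormal values are primary output. No data monitoring committee stands behind them.

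Repeat readings are not taken at random. A high reading invites a second; a normal one does not. If the second alone is analysed, high values get a chance to fall back and normal values get no matching chance to rise. An abnormal ECG taken unscheduled in mid-period, perhaps because of symptoms, loses its place as soon as the scheduled visit takes place.

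The SAP does use a worst-value rule, in Section 17, but only for shifts in Sequence C and in the pooled JZP-110 group, and only over end-of-period values. No single-dose column has a worst on-treatment count.

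**Working it through.** No figure in the plan is at stake, so the main check sets the 6.3 rule against each safety output.

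| Output | High value followed by a normal repeat at the same timepoint | Mid-period unscheduled abnormal value |
|---|---|---|
| ECG incidence and shift (SAP 17.3) | Not counted | Not counted if the scheduled visit exists |
| Temperature, respiratory rate, weight shifts (17.4.1) | Not counted, by default of 6.3 | Not counted |
| Seated blood pressure and pulse incidence and shift (17.4.2) | Averaged in, so diluted but not discarded | Not counted, since only end-of-visit readings are used |
| Laboratory (17.2; SAP 3.6) | No by-dose abnormal-value table | No by-dose abnormal-value table |

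A repeat that confirms the abnormality is still counted in every row that has a table.

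Two details of 6.3 need settling. First, Protocol Appendices 3 and 6 schedule a pre-dose and a post-dose ECG on the same day. Read literally, the latest-time rule would drop the pre-dose ECG, which 17.3 needs for its pre-dose to post-dose tables. The rule must be meant to work within a timepoint, but it does not say so. Second, Table 4 closes the last treated window on the day of the last dose, so an early-termination reading after that day falls into Safety Follow-up and not under the dose.

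**Illustration of size.** The inputs p and ρ are assumptions, because the documents give no repeatability data. Let p be the chance that one reading crosses a limit, ρ the correlation between two readings (bivariate normal), c = Φ⁻¹(1 − p), and 21 + 21 = 42 the subjects randomised to Sequences A and B.

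(a) Same-timepoint repeat, taken whenever the first reading is flagged. A worst-value rule counts p; the latest-value rule counts P(both > c). At p = 5%, the worst-value count is 42 × 0.05 = 2.1 subjects.

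| ρ | P(both > c) | Counted of 42 | Share of first flags lost |
|---|---|---|---|
| 0.3 | 0.0071 | 0.3 | 86% |
| 0.5 | 0.0122 | 0.5 | 76% |
| 0.7 | 0.0196 | 0.8 | 61% |
| 0.9 | 0.0319 | 1.3 | 36% |

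The share lost is 1 − P(both > c)/p; for ρ = 0.5 that is 1 − 0.0122/0.05 = 76%. Over p = 2% to 10% and ρ = 0.3 to 0.9 it runs from 31% to 92%.

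(b) One mid-period reading plus the end-of-period reading. A worst-value rule counts 2p − P(both > c); for p = 5% and ρ = 0.5 that is 0.10 − 0.0122 = 0.088, or 3.7 of 42. Over ρ = 0.9 to 0.3 it counts 2.9 to 3.9 subjects. The closest-to-target rule counts 2.1.

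(c) Mean of two readings, as for blood pressure and pulse. The flag rate is 1 − Φ(c/√((1 + ρ)/2)), which for p = 5% is 2.1% to 4.6%.

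**The case against.** The strongest reply is that little is hidden. The listings hold every value, SAP Section 6 puts the dose at the time of each assessment in them, and with about 49 subjects a reader can count by dose. Clinically significant ECG and vital-sign changes are adverse events (Protocol 6.14.1), reported under the treatment being received. This stands, but a listing is not a tabulated incidence, and the adverse-event route depends on the investigator's judgement.

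It can also be said that 6.3 summarises scheduled assessments by nominal visit, so the first scheduled ECG might keep its place. That sits awkwardly with the rule for repeats and retests. It would not rescue mid-period values either, which 17.3 and 17.4.2 exclude by fixing their outputs at the end of the period.

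Four stronger readings are tempting and are not supported:

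- *That each exceedance is repeated the same day, so the count falls from p to p².* Protocol 6.14.5 asks for two ECGs only before a QTcF discontinuation, with a limit of 470 msec for females, and does not say same day. The SAP tables also use core-laboratory values, while the site assesses ECGs locally, so the reading that prompts a repeat need not be the one analysed.
- *That the counts are simply biased low.* With a true QTcF of 445 msec and an assumed within-visit SD of 8 msec, 27% of first readings exceed 450 and 7% are confirmed. No true value exceeds the limit, so the lost 20 points are measurement noise. At 455 msec (73% against 54%) the under-count is real.
- *That the loss is greatest at the dose with most high readings.* Under the same assumptions the share lost falls, from 73% to 50% to 27%, as the true value goes from 445 to 450 to 455 msec. The absolute loss p − p² is 0.195, 0.250 and 0.195, which is not a rising gradient.
- *That the SAP contradicts the protocol.* Protocol 9.13.4 plans ECG summaries by post-baseline visit and leaves the algorithms to the SAP.

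**Conclusion.** The point holds for ECG incidence and shift tables, and for temperature, respiratory rate and weight shifts: a superseded high value and a mid-period abnormal value do not reach the by-dose counts. For seated blood pressure and pulse it holds only for mid-period unscheduled values. It does not apply to laboratory data.

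This is a gap in the completeness of the descriptive safety tables, not an error in any inference, since none is planned for safety. Its size cannot be derived from the documents. The 31% to 92% range rests on assumed flag rates, assumed correlations and the assumption that every flagged reading is repeated. If repeats are rare or usually confirm the first reading, the effect is small. A reader might infer that all vital-sign and laboratory outlier counts are compromised; the averaging in 17.4.2 and the absence of a laboratory table rule that out.

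**What to change.** 1. In SAP 6.3, limit the closest-to-target and latest-time rule to by-visit descriptive statistics, and state that the same-day rule works within a scheduled timepoint.
2. In SAP 17.3 and 17.4, keep the end-of-period tables and add by-dose incidence and worst-shift tables. Use the most extreme value from the first dose of the period to the day before the first dose of the next, including unscheduled, repeat and early-termination values, assigned to the treatment being taken. State where the interval ends for the last period a subject receives, given how Table 4 closes that window.

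Amending 6.3 alone would not be enough, because 17.3 and 17.4.2 fix their outputs at the end-of-period visit. The cost is a few sentences, one analysis flag and a small set of extra tables; no new data are needed.

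The downside is that rates rise somewhat in every column, placebo included, and subjects with more readings have more chances to be counted. Sequence C contributes four placebo periods per subject, against one in Sequences A and B. Showing placebo by sequence, as SAP 17 already plans, keeps that visible.
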